Challenging the inflammatory response system: Are individuals with insomnia more reactive?

NCT02261597

Date: 02/26/2016

PART B

STUDY DESCRIPTION

TITLE OF PROTOCOL	Challenging the inflammatory response system: Are individuals with insomnia more reactive?
Principal Investigator	[name] PhD

B1. PURPOSE OF PROTOCOL

Primary objective: To investigate the inflammatory response to a physiological stress challenge in insomnia disorder. We expect that individuals with insomnia are more reactive, as manifested in a stronger response of inflammatory systems markers (interleukin [IL]-6, prostaglandin [PG]E2) to a physiological stress challenge (cold pressor test). In accordance, we expect a stronger autonomic (blood pressure, heart rate) and hypothalamus-pituitary-adrenal (HPA, cortisol) response to challenge in insomnia disorder compared to healthy controls.

Secondary objective 1: To investigate the ability to habituate to a repeated physiological stress challenge. We expect that the process of habituation is deteriorated in insomnia compared to healthy controls, as indicated by the lack of the inflammatory, autonomic, and HPA responses to decrease upon repeated exposure to the cold pressor test.

Secondary objective 2: To investigate whether the inflammatory response to challenge can be predicted by the sensitivity of immune cells to glucocorticoids. We expect that in insomnia, monocytes are less sensitive to the counter-inflammatory signal of cortisol, resulting in an exaggerated inflammatory response to a physiological stress challenge.

B2. SIGNIFICANCE AND BACKGROUND FOR THE STUDY

Sleep is critical for the regulation and maintenance of biological systems, and sleep deficiency, such as insomnia, has been shown to be associated with elevated risks for cardiovascular, metabolic, and mood disorders¹¹.

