In this light, the primary objective of this proposal will investigate whether the inflammatory, autonomic, and HPA systems are more reactive to a physiological stressful challenge in insomnia disorder compared to healthy controls.

Beside the hypothesized changes in the system's response reactivity in insomnia, the secondary objective 1 of this proposal will investigate the ability of system's responses to habituate to repeated stressful challenges. Habituation, or a decreased response following repeated exposures to a stressful challenge, is a key feature of the adaptive nature of many biological systems, and has been observed in response to a variety of psychological and physiological stressors and challenges in both humans and animals¹⁵. Considering that most individuals have to deal with stressful challenges on a daily basis, failure of systems to habituate to such daily challenges may elevate disease risk in the long term¹⁵. To test the degree of habituation, we will repeatedly administer the CPT and measure the inflammatory, autonomic, and HPA response magnitude after each challenge.

In summary, this proposal focuses on system's reactivity to challenge (primary objective) and the ability of systems to adapt to repeated challenges (secondary objective 1), rather than assessing basal systems activity only. Dysregulation of systems reactivity and habituation are likely to constitute processes that may serve as valuable predictors of disease risk in insomnia.

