forearm. The participant will click a mouse when they feel the thermode temperature change from neutral to warm and then hot to painful. The pressure pain threshold will be measured by electronic pressure algometer (Somedic Sales AB, Hörby, Sweden. Participants will press a control button when they experience the first sensation of pain. The reactivity and habituation assessment will take place at 1pm. The cold pressor test (CPT) will be administered 3 times. As detailed under procedures, participants will be instructed to immerse their hand in ice-cold water kept at 3 degree C, for a duration of 1min. the interval between the three cold pressor tests will be 1.5 hours. Blood will be sampled after the 1st, 2nd, and 3rd cold pressor test twice, 20min and 50min after hand removal from the cold water bath (these timepoints have been shown sensitive to capture increases of cortisol and IL-6). Urine will also be collected during and after the administration of the cold pressor test series, starting at 1pm and closing out at 6pm.. Prior to, during, and after the cold pressor series, participants will rate their stress levels as well as the unpleasantness of the cold sensation induced by the CPTThe final pain modulation tests, temporal summation and conditioned pain modulation will occur at 500pm. Temporal summation of pain is frequently used as an index of central sensitization of dorsal horn neurons⁵⁶, and will be assessed using the Somatosensory Analyzer (Medoc, Minneapolis, MS). The participant wil have the thermode placed on forearm volar skin of the arm not used for blood draws. Four sequences each consisting of ten brief consecutive heat pulses will be applied via a thermode with a pulse-to-pulse interval of 2.5 sec. Conditioned pain modulation assesses the principle of 'pain inhibits pain', and is a measure of the pain-inhibitory capacity of the central nervous system. The participant will have the thermode placed on the forearm volar skin not used for blood draws...For the test, the test stimulus will be the TS sequence at highest tolerable temperature, applied to the outer volar surface of the non-dominant forearm, along C8-T1 innervations. Immersion of the contralateral foot into a painfully hot water bath (47 °C, Techne® water baths, Bibby Scientific US, Burlington, NJ) Prior to discharge, participants will receive a dinner shortly after 6pm.

Procedures:

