a higher GC sensitivity and this mechanism may contribute to the proposed stronger inflammatory reactivity in insomnia disorder. Measures will be performed once at baseline, using the 2pm blood. Autonomic markers: Blood pressure (BP) measurements will be collected during baseline, throughout the testing sessions and recovery period of the experimental visit, using the dinamap system. Physiological stress challenge - cold pressor test (CPT): A trial CPT will be administered during the initial screening to identify any previously-unrecognized incidence of Raynaud's phenomenon or inability to tolerate the ice bath. The CPT will be administered three times during the experimental visit, starting at 1pm. Throughout the testing and recovery period (until 6pm), the participant will remain in a seated position in a comfortable chair. The CPT will be performed using the hand/arm that is not being used for blood sampling in order to prevent interference. A series of three CPT tests will be applied with an inter-test interval of 60min. Repeated administrations of the cold pressor test have been performed in previous studies (with intervals as short as 2min^{8;13}), but without investigating system's responses. For the current study purposes, an inter-test interval of 60 min has been chosen to capture response increases of IL-6 and cortisol^{8;9;16}. For each CPT test, participants will be asked to insert their hand in a temperature-controlled water bath (Techne® water baths, Bibby Scientific US, Burlington, NJ), kept at 3 degree C, and instructed to leave their hand in for a duration of 1min (participants are told that they can take their hand out earlier if the sensation is getting unbearable). Blood will be drawn 20 and 50min after hand removal from the cold water bath. These time points have been shown sensitive to capture peak cortisol levels as well as significant IL-6 increases^{8;9;16}. Participants will rate the unpleasantness of the sensation prior to hand immersion into the cold water bath, and continue with ratings at 10sec intervals during and after the testing period (up to 3min posttestina).

Pain threshold testing details:

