Twenty sec after foot immersion into hot water bath (47 °C, the conditioning stimulus that is supposed to activate descending pain-inhibitory circuits), the participant rates the intensity of heat pulses (test stimulus, individually tailored to highest tolerable temperature) applied to the forearm.

inhibitory circuits and thereby decrease the perceived pain of the forearm test stimulus (see **Figure 2** for setup).

In total, four CPM trials will be performed: two trials using a hot water bath (47 °C) and two baseline trials without a water bath. For each hot water bath trial, the participant's foot will be first submerged in the water bath. After 20sec of immersion, the 10-pulse temporal summation sequence will be applied to the forearm and the participant will be prompted to rate the pain intensity of the 1st, 4th, 7th, and 10th stimulus using the VAS. There will be a two-minute rest period between all trials during which the thermode will be systematically moved from the distal to proximal sites along the C8-T1 innervated skin in order to avoid re-stimulation of the previously sensitized skin. For statistical analysis, ratings of the two 10-pulse sequences under the conditioning stimulus (hot water) will be averaged, and contrasted against ratings from the baseline (no-water) condition. A decrease in pain intensity ratings under the hot water condition compared to the no-water condition will be used as an index of the pain-inhibitory capacity.

B. Statistical Considerations

Sample Size Justification: For sufficient statistical power, we will need to have 20 participants with a diagnosis of insomnia disorder (based on DSM-V criteria), and 20 healthy control sleepers complete the study protocol (60% women, see power calculation below).

Power calculation

Power calculations were performed for the primary objective of this proposal. With respect to the proposed stronger **inflammatory response reactivity** in insomnia compared to healthy controls, power calculations were based on findings from Heffner et al.¹⁶, reporting a difference in the IL-6 response between poor and good sleepers to an acute challenge of 1.6 pg/ml (SD 1.71 pg/ml, estimated from graph). Thus, we need to study **20 participants in each group** to reach optimal power of 80% (unpaired t-test, alpha = 0.05).

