With respect to the proposed stronger **cortisol response reactivity** in insomnia compared to healthy controls, power calculations were based on findings from Goodin et al.¹⁴, reporting a difference in the cortisol response between poor and good sleepers to an acute challenge (CPT) of 10 units (area under the curve, SD 11 units, estimated from graph). Thus, 80% power will be reached with a sample size of N=20 per group

Statistics: Primary objective: Testing response reactivity to a physical challenge. The overall statistical analysis will be performed within the frame of mixed linear models. Primary and secondary outcome variables pertaining to the primary objective (see above) will constitute the independent variable, time (baseline, 1st CPT post-testing) and group (insomnia vs. healthy controls) will be entered as fixed factors, while subject number will serve as random factor. Simple contrasts will be performed between groups to identify differences at single time points.

Secondary objective 1: Testing response habituation to a repeated physical challenge. Data analysis will be similar as for the primary objective, but the time element will be presented by measures at baseline, 1st CPT post-testing, 2nd CPT post-testing, and 3rd CPT post-testing.

Secondary objective 2: GC sensitivity as a predictor of inflammatory response reactivity. Univariate analysis will be used to identify differences between insomnia and healthy controls in GC sensitivity at baseline. Regression analysis will be used to predict inflammatory response reactivity. Secondary objective 3: Actigraphy-based sleep characteristics as predictors of inflammatory, autonomic, and HPA response reactivity. Univariate analysis will be performed to identify differences in sleep variables (as mentioned under secondary outcome variables above). Regression analysis will

be used to predict response reactivity.

For all analysis, alpha will be set to 0.05.

C. Subject Selection

Human Subjects Involvement and Characteristics

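### Secondary objective 1 (habituation) has no stated test that compares the groups on change from CPT 1 to CPT 3, and the protocol gives two different inter-CPT intervals

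*Combined protocol and SAP*

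**What the plan says.** **The objective.** Section B1 (Secondary objective 1) expects impaired habituation in insomnia compared with controls, shown by "the lack of the inflammatory, autonomic, and HPA responses to decrease upon repeated exposure". Section B2 gives the definition: "Habituation, or a decreased response following repeated exposures to a stressful challenge". The quantity of interest is therefore a between-group difference in change across CPT 1 to CPT 3.

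**The analysis.** Section B3.B, Statistics, describes the primary analysis as a mixed linear model in which "time (baseline, 1st CPT post-testing) and group (insomnia vs. healthy controls) will be entered as fixed factors", with subject as random factor. The tests it names are these: "Simple contrasts will be performed between groups to identify differences at single time points". The habituation analysis is said to be similar, except that "the time element will be presented by measures at baseline, 1st CPT post-testing, 2nd CPT post-testing, and 3rd CPT post-testing". No group-by-time test, change score, slope or habituation index is stated.

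**The power.** Section B3.B, Power calculation: "Power calculations were performed for the primary objective of this proposal".

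**The schedule.** Section B3.A, under the 1-Day CRC Visit: "the interval between the three cold pressor tests will be 1.5 hours". The same section, under Procedures (cold pressor test): "A series of three CPT tests will be applied with an inter-test interval of 60min". The Procedures text repeats 60 min and gives a reason for it, namely to capture the IL-6 and cortisol increases. Both places put blood samples at 20 and 50 min after each hand removal. The PGE2 metabolite is measured in urine collected over the CPT series.

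**The concern.** The primary hypothesis already predicts a group gap after CPT 1. If that gap simply persists, the groups will differ after CPT 2 and CPT 3 even though both habituate identically. A contrast at one of those time points cannot separate a persistent gap from a failure to habituate. Comparing the CPT 1 and CPT 3 verdicts side by side does not help, because with equal true gaps the two can disagree by chance.

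A group-by-time term is arguably implied, since a model with main effects only would give the same group difference at every time point. But the four-level omnibus version of that test includes the step from baseline to CPT 1, which is the primary hypothesis. So no stated or implied test decides secondary objective 1, and the choice would be made after the data are seen.

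The two intervals cannot both be followed. The choice also bears on habituation, because it sets how much of one response may remain when the next CPT starts.

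**Working it through.** **Inputs from the plan (B3.B, Power calculation).** IL-6 response difference 1.6 pg/ml, SD 1.71, 20 per group, unpaired t-test, alpha 0.05. I take the test as two-sided and 1.71 as the SD of the quantity compared between groups, as the plan's own t-test does.

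**Assumption not in the documents.** Within-person correlation ρ between CPTs, taken as 0.5 with a range shown. With SD 1.71 at each CPT:
- SD of change = 1.71 × √(2(1 − 0.5)) = 1.71
- residual SD = 1.71 × √(1 − 0.5) = 1.21

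**1. The plan's own figure.** Standardised difference 1.6/1.71 = 0.936. The t-test needs 19 per group for 80% power, and 20 per group give 82.2%. The stated sample size reproduces and is not in question.

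**2. Equal gap of 1.6 after every CPT, so no habituation difference.**
- *Contrast at CPT 2 or CPT 3.* This is the same t-test as in step 1, so it is significant in 82% of trials, whatever the correlation.
- *CPT 1 and CPT 3 verdicts side by side.* In simulation they disagree by chance in 25%, 21%, 17% and 10% of trials at ρ = 0.3, 0.5, 0.7 and 0.9.
- *Four-level group-by-time omnibus.* The group differences are (0, 1.6, 1.6, 1.6), with mean 1.2. Noncentrality = (20/2) × (1.2² + 3 × 0.4²)/1.21² = 10 × 1.92/1.462 = 13.1. On F(3, 114) this rejects in 86% of trials.
- *Group contrast on CPT 3 minus CPT 1.* The true value is 0, and simulated rejection is about 5% at every ρ from 0.3 to 0.9.

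**3. What the 5% depends on.** The contrast uses levels, whereas habituation concerns responses. Suppose each CPT adds the same 1.6 gap, but a fraction c of the gap persists to the next CPT (c is an assumption). Level gaps are then 1.6, 1.6(1 + c) and 1.6(1 + c + c²).

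| c | Gaps at CPT 1, 2, 3 | CPT 3 − CPT 1 | Rejection, SD of change 1.71 |
|---|---|---|---|
| 0 | 1.6, 1.6, 1.6 | 0 | 5% |
| 0.25 | 1.6, 2.0, 2.1 | 0.5 | 15% |
| 0.50 | 1.6, 2.4, 2.8 | 1.2 | 58% |

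Unequal residual elevation can therefore imitate a habituation difference.

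**4. The interval and carry-over.** Take a 1 pm start, 1 min immersion and intervals counted start to start. The first 50-min sample falls at 13:51. With 60 min the next CPT is at 14:00, 9 min later. With 90 min it is at 14:30, 39 min later. The third CPT starts at 15:00 or 16:00. Both schedules end before 6 pm, so the timetable does not show which interval is meant.

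**5. Power of the right contrast, 20 per group.** The detectable standardised difference at 80% power is 0.909.

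| ρ | SD of change | Detectable at 80% (pg/ml) | Power at 1.6 pg/ml |
|---|---|---|---|
| 0.3 | 2.02 | 1.84 | 68% |
| 0.5 | 1.71 | 1.55 | 82% |
| 0.7 | 1.32 | 1.20 | 96% |

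At ρ = 0.5, if a 1.6 pg/ml difference builds up steadily (0, 0.8, 1.6), the three-level group-by-CPT interaction on F(2, 76) has 74% power, against 82% for the contrast.

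**The case against.** The strongest defence is that the plan never says the single-time-point contrasts decide habituation. They are listed only as a way to locate differences, the analysis is described as similar rather than identical, and the four-level mixed model contains the needed contrast. This stands in part. A reader might infer that the trial will claim impaired habituation from a difference at CPT 3 and be wrong 82% of the time. The documents do not support that, because the plan commits to no such reading. The 82% describes what the named test does if it is used for this question. Nor need the model be replaced. What remains is that no deciding test is named, and the omnibus test an analyst would most naturally reach for mixes reactivity with habituation.

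A second objection is that the remedy has its own weakness, since a contrast on levels is clean only without carry-over. That is correct and changes the fix.

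A reader might also take 1.71 as the residual SD. At a correlation of 0.5 that would put the SD at each time point at 1.71 × √2 = 2.42, which does not fit the plan's use of 1.71 in its own t-test. Figures on that basis are left out.

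Finally, the interval conflict is a protocol inconsistency and does not bear on whether the contrast is missing. It is noted here because it affects how the contrast can be read. The detailed Procedures text favours 60 min, but the overview still says otherwise.

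**Conclusion.** The concern holds as an incompletely specified secondary analysis together with one plain contradiction. The named tests do not answer secondary objective 1. With equal gaps and no habituation difference, a single-time-point contrast is significant in about 82% of trials and the four-level omnibus test in about 86%, against about 5% for CPT 3 minus CPT 1.

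The 82% rests on the plan's IL-6 values. The 86% also needs the assumed correlation of 0.5, and the 5% needs no carry-over. The 58% at 50% carry-over is an illustration, because the documents give no carry-over figure.

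The interval conflict is wrong as written. Naming the contrast is a cheap improvement. Both should be done. Neither touches the sample size for the primary objective.

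**What to change.** 1. Keep the four-level mixed model and include group by time. Make the group contrast on CPT 3 minus CPT 1, with its 95% CI, the deciding habituation test. Report the three-level group-by-CPT interaction (CPT 1 to 3) as supportive only.
2. State that this contrast assumes no carry-over. For blood markers, also pre-specify an analysis of each response relative to its own preceding sample: baseline for CPT 1, and the preceding 50-min sample for CPT 2 and CPT 3.
3. Correct the 1-Day CRC Visit and Procedures texts to one inter-CPT interval. The Procedures text gives 60 min twice with a rationale. If 60 min is kept, item 2 matters more.
4. Name the post-CPT sample (20 or 50 min) used for each blood marker and use the same one at every CPT. Do not use PGE2 from urine pooled over the series for habituation, because it gives no value per CPT.

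**Cost.** A few sentences of analysis text and one protocol correction, with no new samples. The drawback is power. At 20 per group, 80% power needs a habituation difference of about 1.55 pg/ml if the SD of change is 1.71. The analysis in item 2 is less precise. It combines four samples, so with independent residuals its SD is √4 × 1.21 = 2.42 and the detectable difference is 0.909 × 2.42 = 2.20 pg/ml. A null result should be reported as weak evidence, with the interval shown.

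### Five outcomes share the primary objective at 0.05 each, with no defined deciding outcome or multiplicity rule: up to about a 23% chance of any false difference and about 12% of falsely finding greater reactivity

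*Combined protocol and SAP*

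**What the plan says.** B1 (Purpose of Protocol) states one directional primary objective and attaches five outcomes to it. Greater reactivity is to show as a "stronger response of inflammatory systems markers (interleukin [IL]-6, prostaglandin [PG]E2) to a physiological stress challenge (cold pressor test"). The next sentence adds that "we expect a stronger autonomic (blood pressure, heart rate) and hypothalamus-pituitary-adrenal (HPA, cortisol) response to challenge in insomnia disorder compared to healthy controls".

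The Power calculation part of B3.B says "Power calculations were performed for the primary objective of this proposal". It sizes the study on IL-6 at 20 per group "to reach optimal power of 80% (unpaired t-test, alpha = 0.05"), and then gives a second calculation for cortisol, also reaching 80% power at 20 per group. No smaller alpha is mentioned for either.

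The Statistics part of B3.B describes a mixed model with time (baseline, after the first cold pressor test) and group as fixed factors. On which outcomes enter it, the text reads "Primary and secondary outcome variables pertaining to the primary objective (see above) will constitute the independent variable". The model is followed by further comparisons: "Simple contrasts will be performed between groups to identify differences at single time points". The section closes with "For all analysis, alpha will be set to 0.05".

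The available text contains no list that assigns the five outcomes to the primary or the secondary tier, no adjustment or testing order, and no rule for how many outcomes must be positive.

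**The concern.** The primary objective is a single claim, that people with insomnia are more reactive, but up to five tests bear on it and each has the full 0.05. The plan does not say which result settles the claim, or what follows if the markers disagree. A report that rested the claim on whichever marker reached significance would be consistent with the text. The stated 0.05 would then describe each test but not the primary conclusion.

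The power section does not resolve this, because it offers IL-6 and cortisol side by side at full alpha and the analysis section carries over neither as the lead.

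**Working it through.** **Inputs.** From B1: five outcomes, of which two are inflammatory. From B3.B: alpha 0.05 for every analysis; IL-6 difference 1.6 pg/ml with SD 1.71; cortisol difference 10 units with SD 11; 20 per group. Sidedness and the correlations between outcomes are not given. Sidedness is inferred in step 1, and correlations are assumed in step 3.

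**Step 1: reproduce the sample size.** With d = difference/SD, n per group = 2(z for alpha + z for power)²/d².

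- IL-6: d = 1.6/1.71 = 0.936. Two-sided: 2(1.960 + 0.842)²/0.936² gives 18 per group, or 19 with the exact t-test. Power at 20 per group is 82.2% (t-test).
- Cortisol: d = 10/11 = 0.909. Two-sided: 19 per group, or 20.0 with the exact t-test. Power at 20 per group is 80.0%.
- One-sided 0.05 gives 15 per group for both.

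The stated 20 per group is therefore consistent with two-sided tests and not with one-sided tests. A two-sided 0.05 test puts 0.025 in the direction of greater reactivity.

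**Step 2: error rates for independent tests, with no true difference on any outcome.** For k outcomes, the chance of at least one false significant result is 1 − 0.95^k in either direction and 1 − 0.975^k in the direction of greater reactivity.

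| Outcomes counted as primary | Either direction | Greater reactivity |
|---|---|---|
| One | 5% | 2.5% |
| IL-6 and PGE2 | 1 − 0.9025 = 9.75% | 1 − 0.9506 = 4.9% |
| Four (PGE2 set aside) | 1 − 0.8145 = 18.5% | 1 − 0.9037 = 9.6% |
| Five | 1 − 0.7738 = 22.6% | 1 − 0.8811 = 11.9% |

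**Step 3: allow for correlation.** Five outcomes with an assumed common correlation, simulated with 2 million draws from a normal model:

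| Assumed correlation | Either direction | Greater reactivity |
|---|---|---|
| 0.3 | 20.9% | 10.5% |
| 0.5 | 18.3% | 9.1% |
| 0.7 | 14.8% | 7.4% |

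**Step 4: does PGE2 fit the primary model?** The primary model needs a value after the first cold pressor test. PGE2 is measured in urine pooled over the test series: 1pm to 6pm in the description of the experimental day, 3pm to 7pm under Procedures. Neither window gives a separate value after the first test, so PGE2 is not a parallel test in that model as specified.

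**Step 5: power under alternative rules.** Splitting alpha equally between IL-6 and cortisol (0.025 each) lowers IL-6 power from 82.2% to 73.2%. Letting IL-6 alone decide keeps 0.05 and 82.2%. If cortisol is tested at 0.05 only after a significant IL-6 result, the chance that both succeed is 0.822 × 0.800 = 66% if the two are independent (assumption), and higher if they are positively correlated.

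**The case against.** The best defence is that the plan does intend tiers. The Statistics text speaks of primary and secondary outcome variables, and B1 puts the inflammatory markers first and introduces the autonomic and cortisol expectations in a separate sentence. On that reading the lead family is IL-6 and PGE2, and the defect is a cross-reference to a list that does not appear in the available text. This stands in part. It would be wrong to say that the plan has no notion of hierarchy. But the tiers are not filled in, and two outcomes at 0.05 each still double the single-test rate.

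A second defence is that inflammatory, autonomic and hormonal responses are distinct questions in a 40-person mechanistic comparison without a treatment arm, so testing each at 0.05 and reporting all of them is acceptable. That is reasonable for supporting outcomes. It does not say which result answers the one primary objective for which the study was sized.

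A reader might also infer that the chance of falsely claiming greater reactivity is 19 to 23%. The documents do not support that. Such figures describe a false difference in either direction. They would apply to the predicted direction only if each test were one-sided at 0.05, which the stated sample size does not match. Nor does any text say that one positive marker is enough; the plan leaves this open.

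**Conclusion.** The concern holds. The primary objective has no defined deciding outcome and no multiplicity rule, so the error rate of its conclusion cannot be read from the plan. It runs from about twice the single-test rate (9.75% and 4.9% if only IL-6 and PGE2 are primary) to nearly five times (22.6% and 11.9% for five independent outcomes), the first figure in each pair being for either direction and the second for greater reactivity.

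These figures assume two-sided tests, no true differences on any outcome, and a claim made on any one significant result. The correlations are assumptions, and stronger correlation lowers the rates. The unadjusted contrasts at single time points are not counted and would raise them. The study is not invalidated, but the rule should be settled before the data are analysed.

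**What to change.** State in the Statistics part of B3.B that the primary objective is decided by the IL-6 group-by-time contrast, from baseline to after the first cold pressor test, at two-sided 0.05. Because blood is drawn at both 20 and 50 minutes after each test, say how those two values enter the contrast, so that it is one test. List cortisol, PGE2, blood pressure and heart rate as secondary, with nominal p-values, and replace the back-reference with this list. IL-6 is the natural choice: it is named first in B1, powered first in B3.B, and has a value after the first test, which PGE2 lacks.

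This needs no further participants, visits or assays, and IL-6 keeps 82.2% power under the plan's own inputs. It does have a price. A positive result on another marker alone no longer confirms the primary objective, and PGE2, which B1 names beside IL-6, becomes secondary.

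If the sponsor wants a confirmatory cortisol claim, one option is to test cortisol at 0.05 only after a significant IL-6 result. The chance that both succeed is then about 66% if they are independent (assumption), against the 80% stated for cortisol alone.
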